Based on our current practice visit patterns for unduplicated visits by women between age 18 and 49 years, we will have approximately 34,000 eligible visits during the non-screening steps and 34,000 during the screening steps. We have assumed an annual IPV prevalence of 5.5% within the preceding year, based on rates reported by the CDC for SC [17], a screening completion rate of 95%, a 75% counselling rate for women who screen positive, and a 50% referral rate to the Hotline. Studies report the ability of screening to increase patient referral to services from a 2.5 percentage point to an 8.0 percentage point increase based on current referral rates between 0% and 3.6% [18]. Based on an analysis of our archival data, we expect that our current referral rate for IPV for women aged 18-49 seen in our clinics is no more than 0.14% and that this rate will increase to 3.9% with screening.

With about 600 relevant patient visits over 6 months per clinic, 8-12 clinics per wedge, and 3 wedges, we estimate that we will have 97% power to detect an increase in screening (i.e. 0.14% vs. 5.5%), and 89% power to detect a difference in the rate of referral for counseling and/or calls to the Domestic Violence Hotline (i.e. 0.14% vs. 3.9%). While we may be somewhat overpowered for our primary analysis, these numbers of clinics and patients will also allow us to make very precise estimates of the treatment effects within relevant patient subgroups (e.g. whites vs. blacks, urban vs. rural) and to determine whether there are any differential impacts of the intervention on those subgroups. These power calculations are conducted using PASS15 (NCSS, Kayesville, UT) and verified using the 'steppedwedge' function in STATA (StataCorp, College Station, TX), assumed an intraclass correlation coefficient of 0.05 (to account for a moderate level of clustering of patients within clinics), along with an alpha of 0.05 and two-sided testing.

Statistical analysis

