We will use a generalized linear mixed model with a logit link controlling for block set and a fixed effect for each step, as discussed by Hussey and Hughes [19], to compare active screening accounting for the cluster design with a random clinic effect. Primary analyses will also adjust for patient characteristics (age, race) since these have been associated with risk of IPV. Models will be estimated with interaction terms to assess subgroup effects for specific patients, and to examine the effect of practices' characteristics on the heterogeneity of the estimates.

The intraclass correlation coefficients will also be estimated and reported for screening and counselling to assess the assumptions made for the sample size analyses so that this information will be available to future investigations using similar designs and outcomes.

Analysis for the other outcomes will be largely description. Frequency tables with patient demographics, including race, insurance, ethnicity, age, and marital status will be reported. Responses to individual PVS questions will also be presented in the form of frequency tables. Danger 5 risk assessment will be presented using histogram showing counts of patients that scored 0 to 5 of the risks [16]. Physician compliance will be measured as percentage of screened positive patients for whom decision-support templates have been based. Rates of referrals will be reported as percentage from total of patients screened positive.

In addition, we will perform sensitivity analyses to assess the effects of early vs. late randomization, potential “learning” effects that may occur as the screening becomes better integrated in practice routines, the effect of the practices’ presence of a IPV champion prior to the study, and the effect for practice-specific screening refusal and rate of counselling acceptance on the overall estimate. Sensitivity analyses for the primary and secondary outcomes will be conducted using several methods, which have different missing data assumptions: 1) Complete case analyses which assumes missing data are completely at random; 2) Multiple imputation using $M=10$ imputations, which assumes missing at random; and 3) Assigning contrasting age group, race and income category classifications for missing values differentially by intervention group, which aligns with non-ignorable missingness (the data missingness is nonrandom and related to the actual values.)

Follow-up interview

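### Interaction tests for practice characteristics rest on a model that names no clinic-to-clinic variation in the screening effect, so their intervals are too narrow whenever effects vary between clinics and control-period events exist.

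*Combined protocol and SAP*

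**What the plan says.** The Statistical analysis section specifies "a generalized linear mixed model with a logit link controlling for block set and a fixed effect for each step", citing Hussey and Hughes, "to compare active screening accounting for the cluster design with a random clinic effect". It continues: "Models will be estimated with interaction terms to assess subgroup effects for specific patients", and gives as a second purpose of the interaction terms the study of practices' "characteristics on the heterogeneity of the estimates". No other random term, robust variance or small-sample correction is named anywhere in the document.

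Two related items appear in the same section's list of sensitivity analyses: the "presence of a IPV champion prior to the study", and "the effect for practice-specific screening refusal and rate of counselling acceptance on the overall estimate". Neither is said to put clinic-level variation in the effect into the interaction models. Under Power Calculations, the sample is said to allow very precise effect estimates within patient subgroups ("e.g. whites vs. blacks, urban vs. rural").

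**The concern.** With a clinic intercept as the only random term, every clinic that shares a value of the characteristic is given the same screening log-odds ratio. The intercept describes differences in level between clinics. It drops out of each clinic's control-versus-intervention contrast and so cannot stand in for differences in effect. What remains in the standard error is essentially binomial noise from about 600 visits per clinic-step.

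If clinics respond differently for reasons unrelated to the characteristic, that variation is missing from the standard error, and chance differences between two groups of clinics can be reported as effect modification. The Discussion presents the trial as dissemination research, where the kind of practice in which the intervention works is a natural question.

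**Working it through.** **Plan's own figures.** The plan gives no figure for this analysis. The nearest are the powers of 97% and 89%. A parallel comparison of 14 vs 14 clinics, with effective size 14 × 600 / (1 + 599 × 0.05) = 8400 / 30.95 = 271 per arm, gives 96.7% and 87.8%. The inputs can therefore be read as intended. The powers do not bear on this point.

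**Inputs from the documents.** 28 clinics in 3 blocks of 8-12, four half-year periods, about 600 visits per clinic-period, ICC 0.05, two-sided alpha 0.05, rates 0.14% vs 5.5%. The 5.5% is the assumed annual prevalence and the 0.14% is the current referral rate, so the pair is closer to detection than to screening completion.

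**Assumptions.** Blocks of 9/9/10. Between-clinic SD of the effect, τ, from 0 to 1.0 logits. Any control rate other than 0.14%. At a 5.5% mean, one SD either side covers 4.3-7.0% (τ = 0.25), 3.4-8.8% (τ = 0.5) or 2.1-13.7% (τ = 1.0).

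**Step 1, approximate formula.** For a clinic with n0 control and n1 intervention periods, the sampling variance of its log-odds effect is about v = 1/(n0·600·p0·q0) + 1/(n1·600·p1·q1), with q = 1 − p and weight w = 1/v. The planned model uses v; the true variance is v + τ². For a characteristic spread evenly over blocks, true SD / model SE = √(1 + τ²K), with K = Σw²/Σw. The false-positive rate is 2[1 − Φ(1.96/ratio)].

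*Plan's rates.* 600·p0·q0 = 0.839 and 600·p1·q1 = 31.19. Weights are 0.831, 1.634 and 2.329 for one, two and three control periods (9, 9 and 10 clinics). Σw = 45.47, Σw² = 84.46, K = 1.858.
- τ = 0.25: ratio 1.06, false positives 6.4%
- τ = 0.5: ratio 1.21, 10.5%
- τ = 1.0: ratio 1.69, 24.6%

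*Hypothetical 30% to 70%.* Both 600·p·q terms are 126. Weights are 94.5 (19 clinics) and 126 (9 clinics). Σw = 2929.5, Σw² = 312,559, K = 106.7. With 7 of 28 clinics holding the characteristic, model SE = √[(4 + 4/3)/2929.5] = 0.043.
- τ = 0.25: ratio 2.77, false positives 48%
- τ = 0.3: ratio 3.26, true SD 0.139, 55%
- τ = 0.5: ratio 5.26, true SD 0.224, 71%

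**Step 2, simulation.** 1000 trials per cell; 14 vs 14 characteristic with no true modification; random-intercept SD √(0.05/0.95 × 3.29) = 0.416 (ICC 0.05 on the latent logit scale). The planned model was fitted by adaptive quadrature and the interaction tested by likelihood ratio. False positives (%):

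| Control → intervention | τ = 0 | 0.1 | 0.25 | 0.5 | 1.0 |
|---|---|---|---|---|---|
| 0.14% → 5.5% (plan) | 4.6 | 4.5 | 5.8 | 12.1 | 32.7 |
| 0.14% → 50% | 4.9 | 5.7 | 6.3 | 11.2 | 31.9 |
| 5% → 30% | 4.7 | 10.5 | 34.4 | 58.9 | 77.3 |
| 30% → 60% | 5.9 | 15.4 | 51.3 | 71.4 | 84.1 |
| 50% → 95% | 5.2 | 11.2 | 33.6 | 60.5 | 81.3 |

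Monte Carlo SE is about 0.7 to 1.6 points. A smaller run at the plan's rates gave 13% at τ = 0.5.

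**Step 3, same trials with a random clinic-specific screening effect added.** False positives are 3.8-7.5% in all cells against the chi-square reference, and 2.9-6.4% with 26 degrees of freedom. With τ = 0 the planned model is already near 5%. The inflation therefore comes from the omitted effect variation and goes when that variation is modelled.

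**The case against.** The strongest reply concerns size and scope, and much of it stands.

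- **Rates.** The large figures need a control rate of 5% or more, which the documents do not give. At the plan's own rates inflation is negligible up to τ = 0.25. A reader might infer that false practice effects will be common in this trial; the documents do not support that, because they give no value for τ.
- **Primary outcome.** Under Outcome measurement it is the share of eligible patients completing the PVS. The control is a nurse checklist, so read literally this is zero before crossover. There is then no control-versus-intervention contrast and the interaction is not estimable. The concern needs an outcome with control-period events: IPV detection, which Table 1 defines for both screens, or screening completion if nurse-led screens count.
- **Which characteristics.** The plan does not name them. The IPV champion is a sensitivity analysis with no stated interaction, and urban vs rural is offered as a patient subgroup. Both are covered only if analysed as clinic-level interactions.
- **Silence.** The plan does not rule out a random screening effect, and looking for explained heterogeneity does not commit it to unexplained heterogeneity. It is too strong to say that the model contradicts its own purpose. But "accounting for the cluster design with a random clinic effect" is the only random structure given, and an analyst following it would fit the narrow model.

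The mechanism itself is not answered by any of these.

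**Conclusion.** The point holds in conditional form. As written, the interaction models understate the uncertainty of practice-level modifiers whenever the screening effect varies between clinics and control-period events exist. At the plan's rates the model's standard error is too small by a factor of about 1.06, 1.21 or 1.69 for τ of 0.25, 0.5 or 1.0, which gives roughly 6%, 10-13% and 25-33% false positives. The lower ends come from the formula and the upper ends from simulation, except at τ = 0.25, where both give about 6%. For a hypothetical common outcome the factor is about 3 to 5 and false positives are about 50-70%. All of these rest on an assumed τ, and the last also on an assumed control rate.

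A reader might extend this to the main effect of screening or to patient-level subgroups such as race. Nothing shown here supports that; the calculation concerns only characteristics that are constant within a clinic.

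**What to change.** State in the Statistical analysis section that any model testing the interaction of a practice-level characteristic with screening includes a random clinic-specific screening effect as well as the clinic intercept. Have it test the interaction on clinic-level degrees of freedom (28 minus the clinic-level parameters; for example 28 − 2 = 26 for an intercept and one binary characteristic) and report the between-clinic SD of the effect. Apply the same rule to the IPV champion and to urban/rural location if either is analysed as a clinic-level interaction. State also which outcomes these models cover, since PVS completion read literally cannot support them.

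Two substitutes should be avoided:
- A random clinic-by-step term alone is not enough. The clinic-specific effect is shared by all of a clinic's intervention periods, whereas that term treats periods as independent. Simulations of 150-200 runs with common outcomes still gave 17-33% false positives.
- Estimating each clinic's effect separately and regressing the 28 estimates fails for rare outcomes. At 0.14% and 600 visits per period, the chance of no control events is 0.9986^600 = 0.43 with one control period, 0.19 with two and 0.08 with three. About 9 × 0.43 + 9 × 0.19 + 10 × 0.08 ≈ 6 clinics would then have no defined log odds ratio.

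The cost is a short addition to the text, one variance component and wider intervals for practice-level interactions. No new data are needed.
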